8.3 Missing Data Handling

Missing data will not be imputed. Subjects with a missing variable at a particular time point (e.g., a laboratory variable at a visit week) will be excluded from the analysis of that variable at that time point unless otherwise specified.

Section 8.12.2 describes how to deal with partial AE start dates in determining treatment emergence.

Section 8.12.6 describes how to determine prior and concomitant medications with partial medication start dates. Every effort will be made to ensure that the attributes of an AE (seriousness, severity, relatedness to study drug/device/surgical procedure and outcome) are complete. Missing attributes will not be imputed and will be summarized as "unknown".

8.4 Visit Windows

All assessments will be included in the listings. Analytic visit windows will be applied to the following assessments that do not have a visit on the CRF:

Assessments	Analytic Visit
Study drug administration	Day 1
Central radiology	Protocol specified visit windows ¹
Central pathology	Day 1

Analytic visit will be set to the CRF visit for the assessments with a visit on the CRF.

8.5 Pooling of Centers

Data from all centers will be pooled prior to analysis.

8.6 Subject Accountability

Subject accountability will be summarized for the ITT population. Subjects who discontinue tozuleristide prematurely and the reason for tozuleristide discontinuation will be summarized for Arm 2. Subjects who withdraw from the study and the reason for

Confidential Page 19 of 37

study discontinuation will be summarized by treatment arm. The number of subjects who do not undergo surgery will also be summarized by treatment arm.

The number of screen failures and the reason for screen failure will be summarized as a percentage of the all-subject population.

The number of subjects in each analysis population (Section 7) and the reason for excluding from the analysis population will be summarized as a percentage of the all-subject population by treatment arm.

Informed consent (including protocol version), screen failure, eligibility and randomization data will be listed.

8.7 Tissue Biopsy Accountability

Tissue biopsy/specimen accountability will be summarized for the ITT population by treatment arm.

8.8 Protocol Deviations

Subject data will be examined for evidence of protocol deviations in order to assess how well the protocol was followed. This is described in the Protocol Deviations and Non-compliance Management Plan. All protocol deviations will be listed using the ITT population.

8.9 Demographic and Baseline Characteristics

Demographic and other baseline characteristics will be summarized with descriptive statistics by treatment arm for the full analysis population. Demographics include:

- Age at informed consent calculated as Age (years) = integer value of ((Date of Informed Consent Date of Birth + 1) / 365.25),
- Gender,
- Ethnicity, and
- Race.

Baseline characteristics include:

• Baseline weight (kg),

Confidential Page 20 of 37

- Baseline height (cm),
- Baseline body surface area (BSA m², using Mosteller formula),
- Karnofsky performance status,
- Lansky performance status,
- Received prior CNS cancer surgery (Yes, No),
- Time from the most recent prior CNS cancer surgery to current surgery,
- Outcome of the most recent prior CNS cancer surgery (GTR, NTR, STR, Biopsy only, Other),
- Received prior CNS cancer systemic therapy (Yes, No),
- Time from the most recent prior CNS cancer systemic therapy to current surgery,
- Received prior CNS cancer radiation therapy (Yes, No),
- Time from the most recent prior CNS cancer radiation therapy to current surgery,
- Location of current tumor (Brain supratentorial, Brain posterior fossa, Spinal cord, Other),
- Recurrent or progressive disease for current tumor (Yes, No),
- Evidence of metastatic disease (Yes, No)

All baseline data will be listed.

8.10 Medical History

Medical history will be coded by using the Medical Dictionary for Regulatory Activities (MedDRA). Medical history frequencies will be summarized by treatment arm for the full analysis population and will be ordered by descending frequency for total by system organ class (SOC) then, within a SOC, by overall descending frequency of preferred term (PT). If incidence for more than one term is identical, they will be sorted alphabetically.

[figure not shown]
Confidential Page 21 of 37

8.11 Efficacy Analyses

[figure not shown]
8.11.1 Primary Efficacy Endpoints

8.11.1.1 Primary Analyses of Sensitivity and Specificity

The primary efficacy analyses will be based on Group 2 in the full analysis population (Section 7). Each of the 4 sets of statistical hypotheses will be tested at two-sided 5% level (Section 5) using the repeated measures log-linear model specified in this section. Each equivocal tissue specimen from Group 2 that is determined to be either tumor positive or tumor negative by central pathology, and has an image operator assessment and/or a surgeon assessment will be used in the analysis.

[figure not shown]
Confidential Page 22 of 37

[figure not shown]
Confidential Page 23 of 37

[figure not shown]
Confidential Page 24 of 37

Confidential Page 25 of 37

Confidential Page 26 of 37

8.12 Safety Analyses

All safety analyses will be based on the safety analysis population. Safety data collected after re-enrollment for open-label treatment of tozuleristide will be listed.

8.12.1 Exposure to Study Drug

The dose of tozuleristide administrated in volume (mL) and amount (mg) will be summarized as a continuous variable. Dose compliance as measured by the actual dose

Confidential Page 27 of 37

received as the percentage of the intended dose [(Total Volume Infused/Scheduled Volume) x 100] will also be summarized.

8.12.2 Adverse Events

Adverse events will be summarized by the system organ class (SOC) and preferred term (PT) based on the MedDRA dictionary. The actual version will be documented in the CSR.

Adverse events will be defined as treatment-emergent if they are newly occurring or worsen following neurosurgery (Arm 1) or treatment with tozuleristide (Arm 2). Adverse events with incomplete start dates will be considered treatment emergent if:

- Day and month are missing and the year is equal to or after the year of the first neurosurgery for Arm 1 or the first dose date for Arm 2;
- Day is missing and the year is after the year of the first neurosurgery for Arm 1 or the first dose date for Arm 2;
- Day is missing and the year is equal to the year of the first neurosurgery for Arm 1 or the first dose date for Arm 2 and the month is equal to or after the month of the first neurosurgery for Arm 1 or the first dose date for Arm 2;
- Year is missing; or
- Start date is completely missing.

However, if the end date of the AE is before the first neurosurgery for Arm 1 or the first dose date for Arm 2, this AE will not be treatment emergent regardless of the completeness of its start date.

Adverse events will be graded using the NCI CTCAE, version 5.0 if applicable, or the protocol specified severity stated in Section 7.1 of the protocol.

Treatment-emergent AEs, SAEs, severity of AEs, tozuleristide-related AEs, Canvas-related AEs, neurosurgical-related AEs and AEs leading to withdrawal from the study will be summarized by MedDRA preferred term, system organ class and treatment arm for the safety analysis population. In the event of multiple occurrences of the same AE with the same preferred term in the same subject, the AE will be counted once at the greatest severity/relatedness.

The summaries presenting frequency of AEs by SOC and PT will be ordered by overall descending frequency of SOC and then, within a SOC, by overall descending frequency of PT for Arm 2.

Confidential Page 28 of 37

Only the TEAEs from Arm 1 and Arm 2 will be included in the summary tables. All AEs will be included in the listings. Additional listings will be provided for SAEs, AEs leading to death and AEs leading to study withdrawal.

In addition, treatment-emergent AEs for the re-treatment period are defined as newly occurring or worsen following the open-label treatment of tozuleristide. All AEs reported during the re-treatment period will be listed.

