#### 4.1.1 Treatment Allocation

After enrollment, subjects will be randomized 1:10 to Arm 1 (no drug treatment) or Arm 2 (tozuleristide treatment).

Arm 1: Approximately ten subjects (~9% of subjects) will not receive tozuleristide and will undergo standard of care neurosurgery.

[figure not shown]
Arm 2: Approximately 104 subjects (~91% of subjects) will receive tozuleristide at a dose of 15 mg/m^2 administered as a single IV bolus dose at least one hour and no more than 36 hours before the planned start time of surgery.

Re-treatment arm: See Section 4.1.3 below regarding re-treatment.

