# 6.2.3 1 to 36 Hours Pre-Surgery

- ECG (Arm 2 and re-treatment arm only): On the day of tozuleristide dosing, a baseline ECG will be obtained prior to dosing (within 24 hours), and an additional ECG will be obtained 1-30 minutes post-end of dose. ECG recordings will be performed once the subject should have been resting semi-supine for at least ten minutes and will be measured in triplicate over approximately 3 minutes (with wait time of approximately one minute between recordings). A 12-lead ECG recording will be performed in a standardized manner as outlined in the Study Reference Manual. Repeat measurements will be performed if any clinical abnormalities are observed or if artifacts are present.
- Vital signs obtained pre-surgery (Arm 1) or pre-dose and 1-30 minutes post-end of dose (Arm 2 and re-treatment arm).
- Concurrent medications: continuous assessment
- Adverse events: continuous assessment
- Study drug administration (Arm 2 and re-treatment arm only): Tozuleristide is to be administered at least 1 hour (and no more than 36 hours) before the planned start of the surgical excision of the tumor.

[figure not shown]

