# 6.2.5 Day 8 (7 Days Post-Surgery $\pm$ 3 days)

- Performance status
- Physical examination
- ECG (Arm 2 and re-treatment arm only): An ECG will be obtained at seven days postsurgery. ECG recordings will be performed once the subject has been resting semisupine for at least ten minutes and will be measured in triplicate over approximately three minutes (with wait time of approximately 1 minute between recordings). A 12-lead ECG recording will be performed in a standardized manner as outlined in the Study Reference Manual. Repeat measurements will be performed if any clinical abnormalities are observed or if artifacts are present.
- Vital signs
- Concurrent medications: continuous assessment
- Adverse events: continuous assessment
- Measurement of clinical chemistry parameters (Arm 2 and re-treatment arm only)
- Measurement of hematology parameters (Arm 2 and re-treatment arm only)

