#### 7 ADVERSE EVENTS

An AE or adverse experience is any untoward medical occurrence in a subject who is administered an investigational product (whether it is the experimental product or the control) and which does not necessarily have a causal relationship with the investigational product. An AE can therefore be any unfavorable and unintended sign, symptom, or disease temporally associated with the use of a medicinal product, whether or not considered related to the medicinal product. Pre-existing events that increase in frequency or severity or change in nature during or as a consequence of use of a drug in human clinical trials, will also be considered as AEs. AEs may also include pre- or post-treatment complications that occur as a result of protocol-mandated procedures (e.g., invasive procedures such as biopsies).

For investigational medical devices, adverse events are any untoward medical occurrence, unintended disease or injury, or untoward clinical signs (including an abnormal laboratory finding) in subjects, users or other persons, whether or not related to the investigational medical device. An adverse device effect is an adverse event related to the use of the investigational medical device. It can include adverse events from insufficient or inadequate instructions for use, deployment, implantation, installation or operation, or any malfunction of the investigational device.

Any medical condition or laboratory abnormality with an onset date before randomization is considered pre-existing and should be recorded on the medical history CRF page(s).

AEs will be collected from time of randomization through three months after surgery or until start of other tumor-directed therapy, whichever is earlier. After the Day 8 visit, all subjects will be followed by chart review and/or telephone contact if no patient visit is documented every month for three months, or until start of other tumor-directed therapy (chemotherapy, radiation therapy or other investigational therapy), whichever is sooner.

If the patient experiences an AE considered to be related to study products, then the patient will be followed until resolution of that AE or until they are off study (whichever is earlier). An AE does not include:

- Medical or surgical procedures (e.g., surgery, endoscopy, tooth extraction, transfusion); the condition that leads to the procedure is an AE
- Pre-existing diseases or conditions present or detected prior to randomization that do not worsen

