# **Sample Size**

Approximately 114 subjects are planned for treatment in this study.

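### The by-arm adverse event tables set an arm with scheduled ECGs and Day 8 laboratory tests beside an arm with neither, which tilts them against tozuleristide by an unknown amount

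*SAP*

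**What the plan says.** Protocol 4.1.1 sets the arm sizes: "Arm 1: Approximately ten subjects (~9% of subjects) will not receive tozuleristide" and "Arm 2: Approximately 104 subjects (~91% of subjects) will receive tozuleristide".

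The testing schedule differs between the arms. Protocol 6.2.3 limits the ECGs around dosing to treated subjects: "ECG (Arm 2 and re-treatment arm only): On the day of tozuleristide dosing". Protocol 6.2.5 limits the Day 8 ECG in the same way, and the Day 8 laboratory work too: "Measurement of clinical chemistry parameters (Arm 2 and re-treatment arm only"), with a matching line for hematology. SAP 8.12.3 and 8.12.5 repeat the restriction. Arm 1 has Screening chemistry, hematology and coagulation.

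Adverse event collection is not restricted by arm. Protocol 7 and 7.1 collect all events in both arms from randomization to three months after surgery, or to the start of other tumor-directed therapy if earlier. Laboratory abnormalities count as pre-existing only if they began before randomization. The device definition in Protocol 7 expressly covers "untoward clinical signs (including an abnormal laboratory finding) in subjects", and Protocol 6.2.4 has intraoperative imaging in all subjects.

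For the tables, SAP 8.12.2 says that these events "will be summarized by MedDRA preferred term, system organ class and treatment arm for the safety analysis population". Protocol 10.2.8 likewise tabulates treated and untreated subjects. The visible text neither separates events found by a test from events evident clinically nor comments on the unequal schedule.

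**The concern.** An adverse event rate depends on how often events occur and on how hard one looks. Here one arm is looked at harder, by protocol, for one class of event. An abnormal sodium or a prolonged QT interval at Day 8 can be picked up in any Arm 2 subject. In Arm 1 it is picked up only if someone orders the test for clinical reasons.

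With no drug effect at all, the rows for laboratory- and ECG-based terms would still tend to be higher in Arm 2. The rows for any TEAE and for severity would be pulled the same way. The laboratory and ECG parameter summaries are not affected, because Arm 1 has no scheduled post-baseline values to put in them. The problem is confined to the by-arm adverse event tables, where a reader will set adjacent columns against each other and may read part of the difference as toxicity.

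**Working it through.** **Arm sizes.** Protocol, Sample Size: "Approximately 114 subjects are planned for treatment in this study". Protocol 4.1.1: "subjects will be randomized 1:10 to Arm 1 (no drug treatment) or Arm 2 (tozuleristide treatment"). Then 114 × 1/11 = 10.4 and 114 × 10/11 = 103.6, against the stated 10 and 104. As shares, 10/114 = 8.8% and 104/114 = 91.2%, against the stated 9% and 91%. The plan's figures reproduce.

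**Scheduled opportunities to find an event after baseline.**
- Day 8 chemistry and hematology: 0 subjects in Arm 1, about 104 in Arm 2.
- ECG time points after dosing: 0 in Arm 1, about 2 × 104 = 208 in Arm 2, each in triplicate.
- The pre-dose ECG also exists only in Arm 2, but it serves as baseline. It does not itself generate a TEAE.

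**Illustration under no drug effect.** Let p be the proportion of subjects, equal in both arms, with an abnormality that the scheduled tests would find and that would be recorded as an event. Assume full detection in Arm 2 and a fraction d found in Arm 1 by clinically ordered tests. The documents give neither p nor d, so a range is shown.

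Expected subjects: 104p in Arm 2 and 10pd in Arm 1. Spurious difference: p - pd = p(1-d).

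| p | Arm 2 expected | Arm 1 expected, d = 0 / 0.5 / 1 | Gap in points, d = 0 / 0.5 / 1 |
|---|---|---|---|
| 5% | 5.2 | 0 / 0.25 / 0.5 | 5 / 2.5 / 0 |
| 10% | 10.4 | 0 / 0.5 / 1.0 | 10 / 5 / 0 |
| 20% | 20.8 | 0 / 1.0 / 2.0 | 20 / 10 / 0 |
| 30% | 31.2 | 0 / 1.5 / 3.0 | 30 / 15 / 0 |

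These gaps apply to the laboratory- and ECG-based events. In the any-TEAE row the gap is at most p(1-d), because a subject who has another TEAE is already counted there.

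**Precision.** Even with equal testing (d = 1), the chance that none of ten Arm 1 subjects shows such an event is (1-p)^10: 0.60 at p = 5%, 0.35 at 10%, 0.11 at 20% and 0.03 at 30%. An observed 0 of 10 has an exact two-sided 95% upper limit of 1 - 0.025^(1/10) = 31%.

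**The case against.** The strongest reply is that this is a descriptive table in a study whose small untreated arm was not built as a safety control. The protocol justifies the 1:10 arm by selection bias, expectation of fluorescence and the blinded reads. No between-arm safety test is visible. That stands: a reader might infer a formal safety comparison, and the documents do not plan one. Nor does the bias touch the primary endpoints.

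A reader might also infer that Arm 1 is never tested. That is too strong. Arm 1 has Screening laboratory tests, continuous event assessment, a Day 8 physical examination, routine postoperative care, and chart review or telephone follow-up to three months. Clinically ordered tests can produce Arm 1 events, so d need not be 0.

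Three further points stand in part:
- The post-dose ECG precedes surgery, because dosing is at least one hour before the planned start. An argument about abnormalities after neurosurgery covers the Day 8 tests but not that ECG.
- The phrase naming laboratory findings belongs to the device definition, and nothing visible requires every out-of-range value to be recorded as an event. Protocol 7.1.1.1 prefers a diagnosis to individual signs. This may lower p; it does not make detection equal.
- The study calendar and parts of the SAP are not shown, so the absence of a caveat can be stated only for the visible text.

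One reply does not hold. The separate tables for drug-, device- and surgery-related events do not remove the bias. The investigator assigns relatedness, and the stated blinding covers central pathology, central fluorescence assessment and central radiology. Nothing visible blinds the investigator to treatment.

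**Conclusion.** The concern holds as a matter of unequal ascertainment in descriptive tables. Both documents restrict scheduled ECGs and Day 8 laboratory tests to tozuleristide subjects, and SAP 8.12.2 then shows all TEAEs by arm. If detectable abnormalities are equally common in both arms and routine care finds fewer of them in Arm 1 than the scheduled tests find in Arm 2, the tables are tilted against the drug.

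The size is unknown. The illustrative 5 to 30 points (d = 0) and 2.5 to 15 points (d = 0.5) rest on assumed values of p and d and on full detection in Arm 2. They are not estimates of what this trial will show. A reader might take the d = 0 figures as the expected excess, but the documents do not support assuming that routine care finds nothing. With about ten controls, sampling error is of similar size to the bias. This is a minor point about what the safety tables can support, cheap to correct, and not an error in the efficacy analysis.

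**What to change.** SAP section 1 allows amendments before database lock. By then, add to SAP 8.12.2:

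1. A fixed list of TEAE terms whose only basis is a laboratory or ECG value: Investigations terms, plus laboratory-defined terms in other system organ classes such as anemia.
2. By-arm TEAE totals with and without the listed terms, applying the same list to both arms. All Arm 1 laboratory events stay in the full tables and listings. Showing the listed events for Arm 2 alone would discard genuine Arm 1 events.
3. A footnote to every by-arm event table: Arm 1 has no scheduled ECG, including the pre-operative post-dose ECG, and no scheduled Day 8 laboratory tests. A footnote that mentions only post-operative tests would be incomplete.

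For the footnote to be accurate, the Day 8 vital signs should be reconciled too. Protocol 6.2.5 lists them without an arm restriction, while SAP 8.12.4 appears to limit them to Arm 2 and re-treatment.

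The cost is SAP wording, a term list and one repeated table, with no added testing. The limitation is that the list classifies events by type and cannot show how each was detected. An anemia found by routine care is removed from the reduced table along with one found at a scheduled Day 8 draw, which is why both versions are needed.

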8.12.3 Laboratory Parameters

[figure not shown]
All summaries will be based on results in standard international (SI) system units. Reference ranges for all laboratory parameters collected throughout the study are provided by the respective laboratory. A laboratory value that is outside the reference range is considered either high abnormal (value above the upper limit of the reference range) or low abnormal (value below the lower limit of the reference range).

The laboratory reference ranges will be provided on the listings of laboratory data with out of range values flagged (low or high).

Hematology and chemistry laboratory samples are scheduled to be collected at Screening (all subjects) and Day 8 (Arm 2 and re-treatment only). Coagulation laboratory samples will be collected at Screening (all subjects). For hematology and clinical chemistry summary tables, the actual values and change from baseline for each laboratory parameter will be provided by scheduled visit. Summaries will include data from scheduled assessments only, and all data will be reported according to the nominal visit date for which it was recorded (i.e., no visit windows will be applied).

Toxicity grading will follow the NCI CTCAE grades version 5.0. NCI CTCAE toxicity grading will be derived programmatically for laboratory variables where possible. Toxicity grading that requires investigator/clinical input will not be considered and only the numeric criteria will be used for the programmed grade assignments. If this results in the criteria for more than one grade being met, the highest (worst) CTCAE grade will be assigned. Where a result does not meet any of the CTCAE grading criteria, the record will be counted in the 'No Grade' category. For a parameter that can be low or high, e.g. 'hemoglobin increased' or 'anemia', if CTCAE criteria for a grade for 'anemia' is satisfied, then 'hemoglobin increased' will be set to 'No Grade'.

Confidential Page 29 of 37

Confidential Page 30 of 37

All laboratory results in original and SI units will be included in data listings. Tests will be listed in CRF order.

All abnormal laboratory values will be included in the listings.

[figure not shown]
Pregnancy data will be listed.

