### 10.2.8.2 Clinical Laboratory Parameters, ECG and Vital Signs

[figure not shown]
Laboratory parameters will be summarized with descriptive statistics of the change from baseline value by time point. For laboratory parameters defined in CTCAE, shifts of baseline grade to the worse post-baseline grade will also be presented. Subject laboratory values will be listed with toxicity grades and out-of-range flags.

ECG parameters, including QT and QTcF will be summarized with descriptive statistics per time point. Changes from baseline for individual QT/QTcF will be reported as both absolute values (e.g., >450 ms) and relative changes (e.g., > 30 ms). If available, out of range ECG parameters will be assessed for the presence of genetic factors that could contribute to the abnormal ECG findings. ECG data will also be analyzed as a function of pharmacokinetic exposure measures.

Page 78 of 95 BB-006 (PNOC012)

Version Date: 28 Oct 2021

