8.12.5 Electrocardiogram Parameters

Electrocardiogram (ECG) parameters (rhythm, ventricular rate, PR interval, QRS duration, QT interval and QTcF interval) will be collected pre-dose, between 1-30 minutes post-dose and Day 8 and will be summarized with descriptive statistics of the change from baseline value by time point for Arm 2 and re-treatment arm. Overall ECG result (normal or abnormal) will be summarized by time point. Summaries will include data from scheduled assessments only, and all data will be reported according to the nominal visit for which it was recorded (i.e., no visit windows will be applied).

Confidential Page 31 of 37

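### Read literally, the SAP's scheduled-only rule for laboratory summaries reduces the protocol's worse post-baseline grade shift to the Day 8 sample alone

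*SAP*

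**What the plan says.** Protocol 10.2.8.2 sets out two laboratory summaries: change from baseline by time point, and a grade shift. On the second it says: "For laboratory parameters defined in CTCAE, shifts of baseline grade to the worse post-baseline grade will also be presented". It does not confine the shift to scheduled samples.

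SAP 8.12.3 gives the sampling schedule: "Hematology and chemistry laboratory samples are scheduled to be collected at Screening (all subjects) and Day 8 (Arm 2 and re-treatment only". Protocol 6.2.5 agrees, placing Day 8 at 7 days after surgery ±3 days and limiting chemistry and hematology at that visit to Arm 2 and the re-treatment arm.

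SAP 8.12.3 then describes the by-visit tables, in which "the actual values and change from baseline for each laboratory parameter will be provided by scheduled visit". The next sentence is the restriction: "Summaries will include data from scheduled assessments only, and all data will be reported according to the nominal visit date for which it was recorded". It carries no qualifier and no exception. The CTCAE grading rules follow. The visible part of the section does not describe a shift table, and one page of it is blank in the public copy.

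SAP 8.12.5 has a matching sentence for ECGs: "Summaries will include data from scheduled assessments only, and all data will be reported according to the nominal visit for which it was recorded". Protocol 6.2.3 (dosing day) and 6.2.5 (Day 8) require triplicate recordings and add: "Repeat measurements will be performed if any clinical abnormalities are observed or if artifacts are present".

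**The concern.** A worst-grade shift table exists to pick up the most extreme value after treatment, whenever it occurred. With only one scheduled post-baseline draw, a scheduled-only rule leaves no worst value to choose. The sample that remains is taken 4 to 10 days after surgery, so an abnormality in the first post-operative days that resolved before the draw would not show in the table, even if a clinically ordered sample had recorded it.

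Laboratory parameters are a named safety endpoint in both documents (Protocol 10.1.2, SAP 4.2). A reader of the study report would see a table labelled worst post-baseline and reasonably take it to cover the whole post-dose period.

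**Working it through.** **Count of scheduled post-baseline laboratory values** (Protocol 6.2.5, SAP 8.12.3)

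| | Screening | Day 8 | Scheduled post-baseline values per analyte |
|---|---|---|---|
| Arm 1 (about 10 subjects) | yes | no | 0 |
| Arm 2 (about 104 subjects) | yes | yes | 1 |

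Worse post-baseline grade = maximum of the post-baseline grades. With one admissible value, the maximum is the Day 8 grade. With none, as in Arm 1, no shift can be formed. The window is 7 − 3 = 4 to 7 + 3 = 10 days after surgery.

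**Does the restriction reach the shift table?**

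- For: the sentence speaks of summaries without qualification. The section also opens by saying that every summary uses SI units, where the word clearly covers the whole section. The grading rules speak of records being counted in a no-grade category, which is a form of summary, and no visible text exempts it.
- Against: the sentence directly follows the by-visit tables and can be read as qualifying only those. The shift rules may be on the blank page.
- Neutral: the SAP's one visible rule on the worst grade settles which grade to give a single result that meets the criteria for several. It does not take a maximum over time.

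The literal reading is therefore available and perhaps the more natural one, but it is not certain.

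**Illustration of what a single Day 8 draw can see.** The documents state no figure here. Assumptions: the abnormality starts on the day of surgery, its duration is exponential with mean m days, and the draw falls uniformly between 4 and 10 days later.

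P(still present at the draw) = (1/6) ∫ from 4 to 10 of exp(−t/m) dt = (m/6)[exp(−4/m) − exp(−10/m)]

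| m (days) | Calculation | P(present) |
|---|---|---|
| 2 | (2/6)(0.1353 − 0.0067) | 0.043 |
| 3 | (3/6)(0.2636 − 0.0357) | 0.114 |
| 5 | (5/6)(0.4493 − 0.1353) | 0.262 |
| 7 | (7/6)(0.5647 − 0.2397) | 0.379 |

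These figures describe the draw schedule. They become a loss attributable to the SAP only for abnormalities that an unscheduled draw recorded in the study database, and the documents do not show how many of those there will be.

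**ECG.** There are two scheduled post-baseline time points (1 to 30 minutes after dosing, and Day 8), each in triplicate. The protocol orders repeats at those same visits. The visible SAP text does not say whether a repeat counts as scheduled, or how triplicates and repeats yield one value per time point.

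**The case against.** The strongest reply is that the restriction qualifies the by-visit tables it follows, and that the shift rules may sit in text the public copy does not show. That stands as a limit on certainty: the point is about the visible rule as worded, and the sponsor can close it by pointing to an exception if one exists. It would be wrong to say that the SAP omits the shift table.

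Second, the information is not lost. SAP 8.4 lists all assessments, and SAP 8.12.3 lists all abnormal laboratory values. Laboratory abnormalities reported as adverse events are graded and tabulated at greatest severity (SAP 8.12.2). This stands and bounds the harm, though neither route replaces the shift summary that the protocol promises.

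Third, early post-operative values also reflect neurosurgery, steroids, blood products and fluids (Protocol 5.6 and 5.6.2.2), and Arm 1 has no scheduled post-operative laboratory draw for comparison. This stands as a caution in interpretation. It is not a reason to label a one-sample value as the worst.

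A reader might infer more than the documents support:

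- That repeat ECGs are dropped and artifact tracings kept. The SAP reports ECG data by the nominal visit recorded, so a repeat entered under that visit may stay in. The acute post-dose ECG is itself scheduled and summarised.
- That the rule contradicts the SAP 8.2 baseline, which takes the latest non-missing pre-treatment value. That definition yields to anything specified elsewhere, and an unscheduled value can define baseline while by-visit rows show scheduled visits only.
- That the SAP leaves out the QTcF threshold reporting of Protocol 10.2.8.2. It may be in blanked text.
- That 62% to 96% of early abnormalities will be missed. That is the complement of the illustration above and not an estimate for this trial.

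**Conclusion.** The point holds conditionally. If the scheduled-only rule governs the shift table, as its unqualified wording allows and nothing visible contradicts, the worse post-baseline grade in Arm 2 is the grade of one sample taken 4 to 10 days after surgery, and Arm 1 contributes no shift. An earlier unscheduled abnormal value would then appear only in listings or, if reported, among the adverse events.

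The size of the effect in this trial cannot be computed. The range of about 4% to 38% still present at Day 8 rests on assumed onset at surgery, exponential durations with means of 2 to 7 days, and a uniformly timed draw. The conclusion concerns a laboratory safety summary and does not touch the primary efficacy analysis. It is worth correcting because it changes a stated rule at almost no cost. For ECGs, the visible text supports only a request for clarification; no exclusion is demonstrated.

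**What to change.** In SAP 8.12.3, keep scheduled-only data for the by-visit tables of actual values and change from baseline. Add that the shift from baseline to worst post-baseline CTCAE grade uses all post-baseline values on record, scheduled and unscheduled. If a rule to that effect already exists in text not shown, a cross-reference beside the restriction is enough.

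State with the table that unscheduled draws are clinically driven and also reflect surgery and supportive care, and that Arm 1 has no scheduled post-operative laboratory draw, so the arms should not be compared on it.

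In SAP 8.12.5, state how triplicates form the time-point value and how protocol-ordered repeats enter it.

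The cost is a few sentences in an amendment before database lock, which SAP section 1 allows, plus minor programming. No new assessments are needed. The drawback is that worst-grade rates will look less favourable than under a Day 8-only table.
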